3.5 Intervention and control group

Trial participants will be randomised to eight hours of either restrictive or liberal supplemental oxygen treatment.

3.5.1 Restrictive oxygen treatment (intervention group)

The restrictive group will receive the lowest dosage of oxygen ($\geq 21\%$) ensuring an arterial oxyhemoglobin saturation (SpO_2) target = 94% either using no supplemental oxygen, a nasal cannula, a non-rebreather mask (non-intubated trial participants) or manual/mechanical ventilation (intubated trial participants). Pre-oxygenation should be done as usual prior to intubation. Only trial participants receiving an $FiO_2 = 0.21$ can saturate $>94\%$.

3.5.2 Liberal oxygen treatment (control group)

The liberal group will for non-intubated trial participants receive 15 L O_2 /min via a non-rebreather mask in the pre-hospital phase, the trauma bay and during intrahospital transportation (in the OR, ICU, PACU and ward, the flow can be reduced to ≥ 12 L O_2 /min if the arterial oxygen saturation is $\geq 98\%$). The liberal group will for intubated trial participants receive an $FiO_2 = 1.0$ in the pre-hospital phase, the trauma bay and during intrahospital transportation (in the OR, ICU, PACU and ward, the FiO_2 can be reduced to $FiO_2 \geq 0.6$ if the arterial oxygen saturation $\geq 98\%$).

3.5.3 Scheme overview of the intervention process

RANDOMISATION Either in the prehospital setting or in the trauma bay	
Restrictive oxygen treatment Intervention	Liberal oxygen treatment Control

	Intubated trial participants Positive end expiratory pressure (PEEP) at physician discretion	Non-intubated trial participants*	Intubated trial participants Positive end expiratory pressure (PEEP) at physician discretion	Non-intubated trial participants*
Prehospital setting or trauma bay	
Connected to ventilator
 
FiO₂: Lowest value ensuring a saturation = 94%
 
Only trial participants receiving an FiO₂ = 0.21 (or lowest possible) can saturate >94%
 
Pre-oxygenation as usual prior to intubation
	
No supplemental oxygen/nasal cannula/non-rebreather mask depending on the saturation
 
If saturation is <94%: Lowest O₂ flow (between 0-15 L/min) ensuring a saturation = 94%
 
Only trial participants receiving no supplemental oxygen can saturate >94%
	
Connected to ventilator
 
FiO₂ = 1.0
	
A non-rebreather mask
 
O₂ flow = 15 L/min

Intrahospital transportation (trauma center to OR, ICU, PACU or ward)	
Connected to transportable ventilator
 
FiO₂: Lowest value ensuring a saturation = 94%
 
Only trial participants receiving an FiO₂ = 0.21 can saturate >94%
 
Pre-oxygenation as usual prior to intubation
	
No supplemental oxygen/nasal cannula/non-rebreather mask depending on the saturation
 
If saturation is <94%: Lowest O₂ flow (between 0-15 L/min) ensuring a saturation = 94%
 
Only trial participants receiving no supplemental oxygen can saturate >94%
	
Connected to transportable ventilator
 
FiO₂ = 1.0
	
A non-rebreather mask
 
O₂ flow = 15 L/min

Operating room	
Connected to ventilator
	
Pre-oxygenation as usual prior to intubation
	
Connected to ventilator
	
Pre-oxygenation as usual prior to intubation

	
FiO₂: Lowest value ensuring a saturation = 94%
 
Only trial participants receiving an FiO₂ = 0.21 can saturate >94%
 
Pre-oxygenation as usual prior to intubation
	
After intubation: Ventilator
 
FiO₂: Lowest value ensuring a saturation = 94%
 
Only trial participants receiving an FiO₂ = 0.21 can saturate >94%
	
FiO₂ can be reduced to ≥0.6 if the arterial oxygen saturation is ≥98%
	
After intubation: Ventilator
 
FiO₂ can be reduced to ≥0.6 if the arterial oxygen saturation is ≥98%

ICU or PACU or ward
	
Connected to ventilator
 
FiO₂: Lowest value ensuring a saturation = 94%
 
Only trial participants receiving an FiO₂ = 0.21 can saturate >94%
 
Pre-oxygenation as usual prior to intubation
	
No supplemental oxygen/nasal cannula/non-rebreather mask depending on the saturation
 
If saturation is <94%: Lowest O₂ flow (between 0-15 L/min) ensuring a saturation = 94%
 
Only trial participants receiving no supplemental oxygen can saturate >94%
	
Connected to ventilator
 
FiO₂ can be reduced to ≥0.6 if the arterial oxygen saturation is ≥98%
	
A non-rebreather mask
 
O₂ flow can be reduced to ≥12 L/min if the arterial oxygen saturation is ≥98%

The duration of the intervention is eight hours.

All trial participants will have two arterial blood gasses (ABGs) drawn within the intervention period in order to adjust supplemental oxygen treatment according to allocation.

The 1st ABG will be drawn at **hour 1 ± 30 minutes (T1)** after randomisation (initiation of intervention is considered hour 0). If an ABG is not obtainable at T1 due to still being pre-hospital or other circumstances, the ABG must be obtained as soon as possible.

The 2nd ABG will be drawn at **hour 6 ± 2 hours (T6)** after randomisation.

**In case non-intubated trial participants require intubation, this is done and the study is continued for intubated trial participants in the same arm.*

3.5.4 Tracking of oxygen

Oxygen administration and saturation for ventilated trial participants is automatically tracked through the ventilator and transferred to the electronic medical record. The caregiver will note it in a document made specifically for this study (“Randomisation, data collection sheet and REDCap inclusion”, appendix 9).

For non-ventilated trial participants, caregivers will track oxygen dosages and saturations every hour and note it in a document made specifically for this study (“Randomisation, data collection sheet and REDCap inclusion”, appendix 9).

3.5.5 Other treatment

All other drugs administered to the enrolled trial participant will be given as per usual.

3.5.6 Withdrawal from the study

In accordance with the Helsinki Declaration, trial participant’s/trial participant’s next-of-kin consent can be withdrawn at any time, for any reason. Likewise, the investigator can also withdraw trial participants from the trial at any time. The reason for withdrawal will be noted in the electronic Case Report Form.

3.5.7 Participant timeline

Please see figure 1.

3.6 Outcomes

3.6.1 Primary outcome

The primary outcome will be the incidence of 30-day mortality and/or major respiratory complications (pneumonia and ARDS) within 30 days (combined endpoint).

3.6.2 Secondary outcomes

The secondary outcomes will include:

- Mortality at 30 days and 12 months after trauma
- Major respiratory complications (pneumonia and ARDS) within 30 days
- HOS LOS, ICU LOS and days alive outside the ICU
- Time on mechanical ventilation (until 30 days), days alive without mechanical ventilation and number of re-intubations within 30 days
- Pneumonia post-discharge within 30 days
- Episodes of hypoxaemia during intervention (saturation <90%)
- Surgical site infections within 30 days
- EQ-5D-5L score at 6 and 12 months post-trauma
- GOSE score at 6 months and 12 months post-trauma

3.7 Data collection methods, registration and monitoring

Oxygen dosages and saturations will be recorded every hour and noted in a paper data collection sheet specifically made for this study (“Randomisation, data collection sheet and REDCap inclusion”, appendix 9).

Further data collection will be obtained by accessing the trial participants’ medical records. Data points will include:

- Patient characteristics: Name, unique patient identifier (Danish Central Personal Register Number (“CPR nummer”), age, sex, height, weight
- Pre-hospital circumstances: Vital signs, trauma mechanism, details on supplemental oxygen in the pre-hospital phase (indication, SpO₂, supplemental oxygen yes/no, intubation yes/no, oxygen flow/FiO₂), Injury Severity Score (ISS), complete list of injuries, transportation mode to the trauma bay
- Time points: Date and time of trauma, on-scene arrival and departure, trauma bay arrival, ICU/ward arrival, time of intubation/extubation/re-intubation for intubated trial participants, time of surgery, duration of surgery
- Hospital and ICU length of stay
- Vital signs on arrival to the trauma bay, including arterial blood gas analysis if available
- In-hospital variables (pneumonia, ARDS, other infections (surgical site infection or sepsis))
- Ischaemic events (myocardial infarction or cerebral ischemia)
- Adverse Events (AE) and Serious Adverse Events (SAE)
- Co-morbidities prior to trauma: Categorized in heart disease, lung disease, other diseases
- Active smoker (yes/no)
- Specifics of possible brain injury (type and extent) and other cerebral complications such as cerebral ischemia
- Date of death

Trial participants with traumatic brain injury admitted to a neurosurgical intensive care unit can be monitored according to standard practice in the local facility. It is acceptable, but optional, to perform continuous intraparenchymal brain oxygen measurements. Brain oxygen measurements are influenced by placement of the catheter and often less reliable in the first hours of measurement, hence only a factor in a fraction of the eight-hour intervention period in TRAUMOX2.

For all TRAUMOX2 trial participants, it is possible to deviate from the protocol if clinically justified by the treating physician. Such deviations should always be documented including the clinical justification in REDCap.

Mortality status will be collected through registries if possible or according to local practice. EQ-5D-5L score and GOSE score will be collected through telephone interviews, either with the trial participant or with the trial participants next-of-kin or caregiver. Possible pneumonia post-discharge will be evaluated through medicines prescribed after hospital discharge in countries where this information is available.

All trial participants will have two arterial blood gasses (ABGs) drawn during the intervention. The 1st ABG will be drawn at hour 1 ± 30 minutes (T1) after randomisation (initiation of intervention is considered hour 0). If an ABG is not obtainable at hour 1 due to still being pre-hospital or other circumstances, the ABG must be obtained as soon as possible. The 2nd ABG will be drawn at hour 6 ± 2 hours (T6). If more than two ABGs are collected during the intervention (ABGs not related to the study), the ABGs closest to the specified time slots (T1 and T6) should be used for data entry.

3.7.1 Establishment of a biobank for future research

When consent is obtained from a trial participant or from a trial participant's next-of-kin to participate in TRAUMOX2, we will also ask in an additional and separate consent form, not directly related to this research project, if the trial participant wishes to participate in a biobank containing their blood established for future research. The data authorities in Denmark will be applied for storage and the informed consent from the trial participant/trial participant's next-of-kin will be digital in REDCap. It is optional whether the participating centres contribute to the biobank. The management of this biobank will follow the laws of GDPR (in Danish it is called "databeskyttelsesforordningen og databeskyttelsesloven") until a specific research question is established and a research protocol is made. Thus, an application for the permission of a specific research project will be handed in to the "Regionale Videnskabsetisk Komité". In this way, a permission will be sought to do research on the biobank material without obtaining consent from the trial participants again.

3.7.2 Data management

All the above data will be stored in an electronic, web-based, secure, centralised, user-friendly interface using a data collection sheet in REDCap²⁰ specifically made for this trial. This data management system is secure, fully compliant with all regulatory guidelines and a complete audit-trail for data entry validation. Trained members of the research team will be responsible for data collection and entry into REDCap using local electronic clinical registries. Therefore, the electronic case report form (eCRF) will be digital. In case of system malfunction, a paper version of the data collection sheet ("Randomisation, data collection sheet and REDCap inclusion", appendix 9) will be available. The REDCap database will be set up from Rigshospitalet in the the Capital Region and participating centres will be invited to data entry in this database.

External monitoring of registered data will be applied at all trial centres following a monitoring plan developed in collaboration with the good clinical practice (GCP) unit at Copenhagen University Hospital according to GCP standards. Furthermore, the laws on "General Data Protection Regulation" (GDPR; in Danish: "databeskyttelsesforordningen og databeskyttelsesloven") will be followed. The data management will be also be registered internally at Region Hovedstadens own data management center The Knowledge Centre on Data Protection Compliance, Health Science and Innovation. The investigators of the trial will handle all information confidentially (tavshedspligt).

3.7.3 Data definitions

Pneumonia will be defined as per the CDC criteria.²¹

ARDS will be defined as per the Berlin definition.²²

Traumatic brain injury will be defined as²³:

- Severe: AIS \geq 5
- Moderate: AIS 3–4
- Mild: AIS 1–2

3.8 Statistical analysis

In TRAUMOX1, the primary combined endpoint occurred in 20% in the restrictive group and 33% in the liberal group. In larger studies, mortality from trauma has been estimated to be around 6-12%²⁴, and the incidence for ventilator associated pneumonia post trauma to be almost 30%¹³. With 710 trial participants in each arm, we will be able to detect a 33% risk reduction with a restrictive supplemental oxygen strategy (with 80% power at the 5% significance level) if the incidence of our primary outcome is 15% in the liberal

group. Our primary analysis will be a modified intention-to-treat analysis, but a per-protocol analysis will also be carried out. A detailed statistical analysis plan, including the pre-specified subgroup analyses, will be made. In the primary analysis, we will exclude trial participants where no injuries are found defined as ISS = 0.

If less than 5% of data required for any specific analysis on primary or secondary outcomes are missing, a complete case analysis will be performed. If more than 5% are missing, and it is concluded that data are not 'missing completely at random' (MCAR criterion),²⁵ inverse probability weighting will be used to correct this bias. A sensitivity analysis on the assumptions used for missing data will be done to verify robustness.

Inclusion of trial participants will end when the goal of 1420 evaluable trial participants has been reached including the 30-day follow up period. This means that the maximum number of trial participants will be 1600 as inclusion will continue during evaluation of the 30-day follow-up. EQ-5D-5L score and GOSE score at 6 months and 12 months will be obtained. Mortality at 30 days and 12 months will also be obtained. The primary composite outcome will be compared between the two groups using logistic regression reported as Odds Ratio (OR) with 95% CI. The primary analysis will be adjusted for age, sex, centre, intubated at randomisation (yes/no), and known pneumonia on admission (under treatment). Secondary outcomes will also be compared between the two groups using Fisher's exact test/Chi² test for categorical data and competing risk survival analyses for continuous data. We will use a 5% significance level. Any changes or additional analyses will be reported.

In the per-protocol analysis, all trial participants with ≥ 1 major protocol violation will be removed. Please see section 3.8.1 for definitions of major protocol violations.

Pre-specified subgroup analyses will be made on trial participants initially intubated (within one hour of the accident) (yes/no), trial participants with ICU admission (yes/no), trial participants with moderate and severe traumatic brain injuries (yes/no), trial participants with chronic obstructive pulmonary disease (yes/no), episodes with hypoxaemia as well as an analysis on trial participants enrolled prehospital versus in-hospital. An analysis adjusted for Injury Severity Score will also be conducted.

The statistical analysis will be performed by a biostatistician.

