Our experiences from TRAUMOX1 reflect the study design of the current trial proposal: TRAUMOX2. In TRAUMOX1 we experienced 24 hours to be slightly excessive to represent only the acute phase post trauma for which reason we will shorten this time-period to eight hours in TRAUMOX2. Furthermore, we found that several physicians had important concerns with the high dosage of oxygen in the liberal arm for which reason the concentration will be reduced. Finally, we did not randomise trauma patients in the pre-hospital phase, but instead on arrival at the trauma bay (median [IQR] time to randomisation: 7 [4-10] minutes, median [IQR] time from trauma to trauma bay arrival: 51 [29.0-67.5] minutes). To limit this inconsistent exposure to oxygen in the pre-hospital phase prior to inclusion we will initiate the intervention in the pre-hospital phase where possible in TRAUMOX2. This is consistent with our hypothesis that a liberal supplemental oxygen strategy may be detrimental and should be avoided as soon as possible. Hence, the study should be initiated in the prehospital setting in alignment with other time critical emergency research studies.

2. Study objectives

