3.4.1 Randomisation and blinding

Trial participants will be randomised 1:1 in variable block sizes and stratified by centre (pre-hospital base or trauma centre) and tracheal intubation at inclusion. The randomisation table will be generated outside of our electronic database REDCap (explained in section 3.7.2) by a biostatistician otherwise not connected to the study. The allocation sequence list and block sizes will only be known by the statistician and will remain

concealed from the investigators. Randomisation will be determined after proxy consent (or according to local legislation in each country) from opening a concealed envelope with information on allocation. The envelopes will be located both pre-hospital and in-hospital. Each concealed envelope will contain a study ID that matches a study ID in the randomisation list generated by the statistician.

The study will be an international, multicentre, parallel-grouped, superiority, outcome assessor- and analyst-blinded, randomised, controlled, clinical trial with regards to treatment: treating staff will be aware of the trial participants' randomisation group. While including trial participants for the study, the research team will be aware of the trial participants' oxygen allocation strategy. However, at least two allocation blinded primary outcome assessors (specialists in anaesthesia, intensive care, emergency medicine or similar) will be appointed at each centre to assess in-hospital lung complications (pneumonia and ARDS). Blinding will be ensured by concealing all information indicative of the allocation prior to assessment. The statistician and manuscript writers will be blinded towards the allocation of treatment once the trial ends when data is being analysed and the manuscript is drafted.

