For intubated trial participants: FiO₂ <0.4 at two consecutive hourly time points on the data collection sheet.

TABLE 3 - PRIMARY OUTCOME AND SECONDARY OUTCOMES

Primary outcome	Unit
Malondialdehyde (MDA) at H24	μM (median)
Secondary outcomes	
Malondialdehyde (MDA) at H _{start} , H8 and H48	μM (median)
Superoxid dismutase (SOD) at H _{start} , H8, H24 and H48	ng/mL (median)
Interleukin-6 (IL-6) at H _{start} , H8, H24 and H48	pg/mL (median)
Interleukin-8 (IL-8) at H _{start} , H8, H24 and H48	pg/mL (median)
Interleukin-10 (IL-10) at H _{start} , H8, H24 and H48	pg/mL (median)
Intercellular adhesion molecule-1 (ICAM-1) at H _{start} , H8, H24 and H48	pg/mL (median)
Vascular endothelial growth factor (VEGF) at H _{start} , H8, H24 and H48	pg/mL (median)
Granulocyte colony-stimulating factor (G-CSF) at H _{start} , H8, H24 and H48	pg/mL (median)

H_{start}, H8, H24 and H48 are evaluated at:

H_{start}: Closest possible time from time of randomisation upon arrival to the trauma centre

H8: After the 8-hour intervention has ended and up to 2 hours after

H24: At 24 hours ± 3 hours after time of randomisation

H48: At 48 hours ± 3 hours after time of randomisation

TABLE 4 - EXPLORATORY SECONDARY OUTCOMES (IN-HOSPITAL VARIABLES)

[figure not shown]
Variable	Definition
30-day mortality (y/n)	
Major respiratory complications (pneumonia* and/or ARDS**) within 30 days (y/n)	Assessed by two specialists in anaesthesia, intensive care medicine, emergency medicine or similar using blinded medical records, laboratory and microbiology results, and radiological assessments
Intensive Care Unit admission (y/n)	
Intubation post randomisation (y/n)	During and after intervention
If yes, location, time and date of intubation	Pre-hospital, Trauma Centre, Intensive Care Unit
	Mechanical ventilation initiated as part of general anaesthesia on spontaneously breathing patients to facilitate surgery is not included
Sepsis during hospital admission (y/n)	Clearly stated in the patient's medical record by a physician or assigned as a diagnosis

*Pneumonia is categorised as non-ventilator-associated pneumonia (PNEU) or ventilator-associated pneumonia (VAP), defined by the CDC criteria³⁴

**ARDS is categorised as mild, moderate, or severe, defined by the Berlin definition³⁵

Figures

CONSORT flow diagram of screening, inclusion and follow-up

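### Main-trial subgroups by ICU admission and by hypoxaemia episodes are defined after randomisation, so their treatment effects can be biased even if oxygen strategy has no effect on the primary outcome

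*Protocol*

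**What the plan says.** Protocol section 3.8 names the main trial's subgroups: "Pre-specified subgroup analyses will be made on trial participants initially intubated (within one hour of the accident) (yes/no), trial participants with ICU admission (yes/no", then "episodes with hypoxaemia as well as an analysis on trial participants enrolled prehospital versus in-hospital". The others are moderate or severe brain injury and chronic obstructive pulmonary disease. None of the first three is tied to status at randomisation. No interaction test and no caution on interpretation is given.

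Elsewhere the documents treat two of these variables as results of care:

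- Section 3.6.2 lists as a secondary outcome "Episodes of hypoxaemia during intervention (saturation <90" per cent. SAP Table 2 (biomarker sub-study) also records hypoxaemia episodes among the data collected during the intervention.
- Section 3.6.2 lists "HOS LOS, ICU LOS and days alive outside the ICU" as secondary outcomes, and SAP Table 4 lists "Intensive Care Unit admission (y/n" as an exploratory one. The treatment scheme in section 3.5.3 places transfer to the ICU after allocation.

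For intubation, section 3.4.1 says randomisation is "stratified by centre (pre-hospital base or trauma centre) and tracheal intubation at inclusion". The primary model in section 3.8 adjusts for intubation at randomisation. Neither is the one-hour definition used for the subgroup.

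**The concern.** Randomisation makes the arms comparable within a subgroup only if membership is fixed before allocation or cannot be altered by it. Hypoxaemia is the clearest exception. The arms differ by design in the saturation they aim for (sections 3.5.1 and 3.5.2), so the intervention acts directly on the variable that defines the subgroup. ICU admission is less direct, but treating staff know the allocation (section 3.4.1) and could be influenced by it.

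Suppose one arm has more hypoxaemic patients because milder cases cross the threshold there. Its hypoxaemic group is then less sick on average. Its non-hypoxaemic group is also less sick, because it has lost its more severe members. Both strata can then favour that arm although the arms do equally well overall. If the restrictive arm has more hypoxaemia, this spurious benefit points the same way as the trial's hypothesis.

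**Working it through.** **1. The plan's own figure.** The plan states no figure for the subgroups. The 710 per arm used below reproduces. With p1 = 0.15, p2 = 0.15 × (1 − 0.33) = 0.1005 and mean 0.12525:

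n = [1.96 × √(2 × 0.12525 × 0.87475) + 0.8416 × √(0.15 × 0.85 + 0.1005 × 0.8995)]² / 0.0495² = 701 per arm.

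Power at 710 is 80.5%. The point does not depend on this.

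**2. Intubation timing.** Section 1 gives the pilot's "median [IQR] time from trauma to trauma bay arrival: 51 [29.0-67.5] minutes" and a median of 7 minutes from there to randomisation. That puts trauma-bay randomisation at about 51 + 7 = 58 minutes. Lognormal and normal fits to the medians and IQRs put about 50% and 53% of such patients inside the first hour at randomisation.

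- For the other half, one-hour status is already fixed when they are allocated.
- For those randomised inside the hour, only intubations between randomisation and 60 minutes can be affected.
- Pre-hospital enrolment widens that window by an amount the documents do not give.
- In-hospital treatment may start up to 90 minutes after arrival (section 3.4), so some intubations made before randomisation but after the hour are missed.

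**3. Hypoxaemia, no effect on the outcome.** All inputs are assumptions. Severity S is standard normal and the same in both arms. Outcome risk = 1/(1 + exp(2.35 − S)), which averages about 12% in each arm. A patient is hypoxaemic if a normal variable with correlation ρ to S exceeds a threshold set to give the stated share in that arm.

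| Restrictive vs liberal | ρ | RR, hypoxaemic | RR, not hypoxaemic |
|---|---|---|---|
| 5% vs 5% | 0.7 | 1.00 | 1.00 |
| 7% vs 5% | 0.7 | 0.94 | 0.97–0.98 |
| 10% vs 5% | 0.7 | 0.87 | 0.94 |
| 15% vs 5% | 0.3 | 0.90 | 0.96 |
| 15% vs 5% | 0.7 | 0.79–0.80 | 0.89 |

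Ranges show simulation against numerical integration. For the last row, integration gives risks of 0.2455 (restrictive) and 0.3085 (liberal) in hypoxaemic patients, and 0.0964 and 0.1088 in the rest. The overall risks agree:

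- Restrictive: 0.15 × 0.2455 + 0.85 × 0.0964 = 0.119.
- Liberal: 0.05 × 0.3085 + 0.95 × 0.1088 = 0.119.

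The overall RR is therefore 1.00, while both strata show a benefit.

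**4. A second model, all three variables.** A latent normal severity drives membership and outcome, with logit slope 1.0 or 1.5 for each. Outcome risk is 15% in both arms. Odds ratios are restrictive vs liberal, shown as slope 1.0 / slope 1.5; the true value is 1.

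| Share in subgroup, liberal vs restrictive | OR, yes | OR, no |
|---|---|---|
| Hypoxaemia 10% vs 15% | 0.94 / 0.88 | 0.96 / 0.92 |
| Hypoxaemia 10% vs 20% | 0.89 / 0.79 | 0.92 / 0.85 |
| Hypoxaemia 5% vs 20% | 0.83 / 0.68 | 0.88 / 0.77 |
| ICU 40% vs 37% | 1.02 / 1.04 | 1.02 / 1.05 |
| ICU 40% vs 35% | 1.04 / 1.07 | 1.04 / 1.08 |
| ICU 40% vs 30% | 1.09 / 1.16 | 1.08 / 1.16 |
| Intubated in first hour 20% vs 19% | 1.01 / 1.02 | 1.01 / 1.02 |
| Intubated in first hour 20% vs 18% | 1.02 / 1.04 | 1.02 / 1.03 |

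With equal shares, or with slope 0, every OR is 1.00. At 710 per arm, the false-positive rate in the non-hypoxaemic stratum is 8% / 15% for 10% vs 20%, and 13% / 32% for 5% vs 20%, instead of 5%.

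**The case against.** **A reader might infer that these subgroup effects are biased even if treatment does nothing.** The documents do not support that. If allocation leaves membership unchanged, or membership is not prognostic, there is no bias, as the equal-share and zero-slope results show. Both conditions are plausible for hypoxaemia and possible for ICU admission, but neither is established.

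**A reader might also class early intubation as simply post-randomisation.** The clock runs from the accident, and about half of trauma-bay patients would have their status fixed before allocation. What stands is the mismatch with the stratum and the model covariate.

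**The sizes rest on assumed rates and correlations.** Section 6.1 reports seven desaturation episodes in the pilot's restrictive arm, most of them in two participants, and gives no liberal-arm figure. The hypoxaemic stratum would also be imprecise. At 15% vs 5% and ρ = 0.7 it holds 710 × 0.15 × 0.2455 = 26 events against 710 × 0.05 × 0.3085 = 11. The standard error of the log RR is √(1/26.1 − 1/106.5 + 1/11.0 − 1/35.5) = 0.30, so a 95% interval spans a factor of about 1.8 either way. The RR of 0.79 shows direction and is not a forecast.

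**The hypoxaemia subgroup has no stated time window.** Reading it as during the intervention relies on section 3.6.2, the only place where the protocol defines such episodes.

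**Section 3.8 promises a detailed SAP covering the subgroups.** The SAP supplied is for the biomarker sub-study, so the main one may refine these definitions or add interaction tests. That limits what can be said about the final analysis, but it does not change the protocol text.

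**Conclusion.** The point holds for two of the three variables. ICU admission and, on the natural reading, hypoxaemia episodes are determined after randomisation and can be changed by allocation. Their within-subgroup effects can therefore be biased with no effect on the primary outcome, provided allocation shifts membership and membership is prognostic. Intubation within an hour of the accident is a mixed variable with small likely bias (OR about 1.01 to 1.04 under the assumed shares).

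Under the second model's assumptions, a true null shows as an OR of about 0.68 to 0.94 among hypoxaemic patients and 1.02 to 1.16 among ICU patients. The ICU direction reverses if the restrictive arm has more admissions. The primary modified intention-to-treat comparison is not affected.

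**What to change.** In section 3.8 and the main-trial SAP:

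- Define the intubation subgroup by the randomisation stratum, intubated at inclusion (yes/no).
- Remove ICU admission and hypoxaemia episodes as treatment-effect subgroups. Report outcomes by them descriptively only, with membership shown by arm.
- If a severity or oxygenation subgroup is wanted, use a value fixed before allocation, such as an ISS split (the sub-study uses ISS above 15) or the first SpO2 where it was recorded before randomisation.
- Test the retained baseline subgroups by treatment-by-subgroup interaction.

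Two limits apply to the optional replacements. A clean record of saturation below 90% before randomisation is not assured. Sub-study SAP Table 1 holds the highest pre-randomisation SpO2 and first vital signs, and the pre-hospital SpO2 in protocol section 3.7 may follow allocation in patients enrolled pre-hospital. An ISS split asks a different question from ICU admission, and section 3.8 already plans an ISS-adjusted analysis.

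The cost is wording only, with no new data. The ICU and hypoxaemia breakdowns lose their standing as treatment-effect subgroups.
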